6.12.3. Deaths, Other Serious Adverse Events, and Other Adverse Events for Review

Treatment-emergent AEs by Preferred Term will be reported.

The full summary of AEs is described in the CPMP SAP Version 5.

6.12.4. Clinical Laboratory Evaluation

The general analysis of laboratory parameters is described in the CPMP SAP Version 5.

In this ISA, laboratory results will be reported for the first 4-week, active-treatment period and separately for the entire 8-week study period.

Study OA02 will also consider the following analyses of laboratory analytes used to assess renal function. The planned summaries for these analytes are the same as those that have been described in the CPMP SAP; however, the reporting of these analytes will be separate from the general analysis of laboratory parameters.

Renal data analyses:

- Serum creatinine (change from baseline in mg/dL)
 - Estimated glomerular filtration rate (eGFR; Chronic Kidney Disease Epidemiology Collaboration [CKD-EPI] algorithm using serum creatinine). Algorithm provided by the central laboratory.
 - For eGFR calculation, we will summarize shift tables of eGFR changes for baseline versus postbaseline by minimum, maximum, and last observed eGFR result.
 - i. Category 1: Normal or increase in GFR ($90 \text{ mL/min}/1.73 \text{ m}^2$)
 - ii. Category 2: Mild reduction in GFR (60 to $89 \text{ mL/min}/1.73 \text{ m}^2$)
 - iii. Category 3a: Moderate (a) reduction in GFR (45 to $59 \text{ mL/min}/1.73 \text{ m}^2$)
 - iv. Category 3b: Moderate (b) reduction in GFR (30 to $44 \text{ mL/min}/1.73 \text{ m}^2$)

- v. Category 4: Severe reduction in GFR (15 to 29 mL/min/1.73 m²)
- vi. Category 5: Kidney failure (GFR < 15 mL/min/1.73 m² or dialysis)

Abnormal eGFR is specified below and will be summarized in the laboratory summary tables:

Abnormal low: <90 mL/min/1.73 m²

Abnormal high: as specified by the central laboratory.

6.12.5. Vital Signs and Other Physical Findings

The analysis of vital sign parameters is described in the CPMP SAP Version 5.

Vital signs will be reported for the first 4-week, active-treatment period and separately for the entire 8-week study period.

6.12.6. Electrocardiograms

The analysis of electrocardiogram parameters is described in the CPMP SAP Version 5.

Electrocardiogram findings will be reported for the first 4-week, active-treatment period and separately for the entire 8-week study period.

6.12.7. Suicidal Ideation or Behavior

Reporting of suicidal ideation or behavior through the Columbia Suicide-Severity Rating Scale (CSSRS) has been described in the CPMP SAP Version 5. The CSSRS results will additionally be reported separately for the first 4-week, active-treatment period.

6.13. Subgroup Analyses

General subgroup analyses are described in the CPMP SAP Version 5.

Study OA02 will also consider the following subgroup analyses for the primary efficacy outcome and key secondary outcome.

Subgroup Variable	Categories
Kellgren-Lawrence Grade	Categories: Grade 2, Grade 3, Grade 4 Note: Alternative groupings may be created based on the number of participants classified within each grade (for example, oeS eH)

The subgroup analyses will be conducted using similar modeling approaches as the primary and key secondary analyses. Additional factors in the model are described in the CPMP SAP Version 5. The treatment difference at the endpoint will be reported within each level of the subgroup factor along with 95% credible intervals. Frequentist MMRM may be performed as a sensitivity analysis using the modeling approach described in the CPMP SAP Version 5.

6.14. Protocol Deviations

Patients with study-important protocol deviations will be summarized by type of deviation and listed by treatment and investigative site.

Important protocol deviations for the study are described in the CPMP and OA02 Trial Issue Management Plans.

6.15. Interim Analyses and Data Monitoring

Safety review will be conducted under the auspices of an Assessment Committee according to the specifications set forth in the protocol. These analyses will be at the CPMP level and will consider data from all ongoing ISAs. Details are provided in the CPMP SAP Version 5.

Interim analyses are planned for Study OA02 to be conducted when 60% of patients have completed the 4-week, active-treatment period. Details of the interim analysis can be found in the Statistical Analysis Center (SAC) SAP. The interim analysis will be conducted by an independent Assessment Committee (AC), and the AC will disseminate interim results, if necessary, in a manner that will not affect the conduct of the ongoing study.

6.16. Planned Exploratory Analyses

The following analyses may be conducted for exploratory purposes:

CCI

6.18. Annual Report Analyses

Analyses will be produced as needed for the purposes of providing periodic safety reviews to regulatory agencies (for example, Development Safety Update Reports). Data from this ISA will be combined with data from other clinical studies that investigated LY3526318. In all analyses, a combined LY arm will be created, which will include participants assigned to any dose of LY3526318 in the included studies, including LY-combination regimens.

The following data will be summarized by treatment group:

enrollment (ongoing and completed)

demographics (race, ethnicity, and gender)

exposure:

- cumulative number of subjects exposed to LY3526318
- cumulative number of subjects exposed to LY3526318 by age
- cumulative number of subjects exposed to LY3526318 by sex
- cumulative number of subjects exposed to LY3526318 by race

cumulative summary of serious AEs.

The following listings will be provided.

list of serious AEs during the reporting period

list of subjects who died

cumulative list of subjects who discontinued because of an AE (discontinued treatment or study)

list of subjects who discontinued due to an AE during the reporting period.

Additional analyses may be added or omitted at the time of report submission as needed.

6.19. Clinical Trial Registry Analyses

Additional analyses will be performed for the purpose of fulfilling the Clinical Trial Registry (CTR) requirements.

Analyses provided for the CTR requirements include the following:

Summary of AEs will be provided as a dataset that will be converted to an XML file. Both Serious AEs and Other AEs are summarized by treatment group and by MedDRA Preferred Term.

A serious AE is an AE that is considered Serious whether or not it is treatment emergent.

An AE is considered in the Other category if it is both a TEAE and is not serious. For each Serious AE and Other AE, for each term and treatment group, the following are provided:

- the number of participants at risk of an event
- the number of participants who experienced each event term
- the number of events experienced.

Consistent with www.ClinicalTrials.gov requirements, Other AEs that occur in fewer than 5% of participants in every treatment group may not be included if a 5% threshold is chosen (5% is the minimum threshold).

AE reporting is consistent with other document disclosures, for example, the CSR and manuscripts.

7. Unblinding Plan

The general unblinding plan is described in the CPMP SAP Version 5 and in the Study CPMP Blinding and Unblinding Plan Version 1. Unblinding considerations specific to Study OA02 are provided below.

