6.1. General Considerations

The estimand for the primary clinical question of interest has been described in the CPMP SAP Version 5.

The key secondary clinical question of interest is: What is the treatment difference between LY3526318 and placebo assessed using mean change from baseline to Week 4 for pain as measured by the WOMAC® pain subscale in participants with osteoarthritis of the knee regardless of initiation of rescue medication or other allowed concomitant medication and assuming that they would have continued initially randomized treatment condition?

Treatment condition: the randomized treatment along with potential use of rescue medication or other allowed concomitant medications regardless of adherence.

Population: participants with chronic pain conditions.

Endpoint: change from baseline to Week 4 in the WOMAC® pain subscale.

Intercurrent events: the intercurrent event is treatment discontinuation for any reason.

Population-level summary: difference in mean changes from baseline between treatment conditions.

The estimand is following a hypothetical strategy where efficacy of LY3526318 is assessed under the assumption that the participants would have continued their initially randomized treatment condition even if they discontinued.

Unless otherwise specified, efficacy analyses will be conducted for the first 4 weeks of the double-blind period (active-treatment phase) and separately for the entire 8-week study. A post active-treatment population will be used for analyses of the last 4 weeks of the double-blind period (post active-treatment phase) and will include all patients who do not discontinue at or prior to Visit 5. For treatment-emergent adverse events (TEAEs), participants in the post active-treatment population will be analyzed according to the treatment they receive during the active-treatment phase. Adverse event (AE) analyses will be reported for the first 4 weeks of the double-blind period (active-treatment phase) and separately for the last 4 weeks of the double-blind period (post active-treatment phase). Some AEs may be reported for the entire 8 weeks if necessary. Laboratory, electrocardiogram, and vital sign results will be reported for the active-treatment phase and separately for the entire 8-week study.

Other general considerations for analyses are described in the CPMP SAP Version 5.

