6.12. Safety Analyses

The general analysis of safety has been described in the CPMP SAP Version 5. However, additional ISA-specific safety considerations are described in the sections below.

6.12.1. *Extent of Exposure*

Duration of exposure (defined as time since first dose of study treatment to last dose of study treatment in days) to study drug will be summarized by treatment group using descriptive statistics; the summary will also include the total exposure in patient years. Extent of exposure will be reported separately for the first 4 weeks (active treatment) and the last 4 weeks (post active treatment) of the double-blind period. All patients will receive placebo starting the day of Visit 5.

Duration of exposure (days):

For the first 4-week, active-treatment period:

= Date of last dose during the active treatment period Date of first dose for the active treatment period + 1.

For the last 4-week, post active-treatment period:

= Date of last dose during the post active-treatment period Date of first dose for the post active-treatment period + 1.

Total exposure in patient years will be calculated as follows:

Total exposure in patient years = Sum of duration (days) of exposures for all patients in the treatment group/365.25.

6.12.2. *Adverse Events*

The general analysis of AEs has been described in the CPMP SAP Version 5.

This ISA will report TEAEs for the first 4 weeks as well as post treatment-emergent AEs (PTEAEs) for the last 4 weeks of the double-blind period. For TEAEs in the first 4 weeks of the double-blind period (active-treatment phase), the baseline will be prior to the first dose date.

A PTEAE is defined as an event that first occurs or worsens in severity after the active-treatment phase (after Visit 5) and on or before study discontinuation. The Medical Dictionary for Regulatory Activities (MedDRA) Lowest Level Term (LLT) will be used in the post treatment-emergent computation. The maximum severity for each LLT during the active-treatment period (Visits 3 to 5) will be used as a reference.

The baseline of PTEAE is from the first dosing date to Visit 5. The post active-treatment phase (after Visit 5) will be included as postbaseline for this analysis. While unusual, it is possible to have a missing severity for events. For an event with a missing severity during the baseline

Events with a missing severity during the post-active-treatment period will be treated as

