, , , PTEAEs will be determined by comparing with the active-treatment period.

PTEAEs will be summarized by Preferred Term and by Preferred Term within System Organ Class in participants who received LY3526318.

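### SAP 6.19 gives non-serious adverse events that are new or worse after Visit 5 no stated place in the registry tables, and SAP 6.12.2 summarises those events in LY3526318 recipients only

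*SAP*

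**What the plan says.** SAP 6.19 sets two different entry rules for the registry tables. For serious events: "A serious AE is an AE that is considered Serious whether or not it is treatment emergent". For the rest: "An AE is considered in the Other category if it is both a TEAE and is not serious". For each term and arm it asks for the number at risk, the number of participants affected and the number of events. It also allows terms below 5% in every arm to be left out, if that threshold is chosen. It names no reporting period and does not mention PTEAEs.

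SAP 6.12.2 divides the double-blind period: "This ISA will report TEAEs for the first 4 weeks as well as post treatment-emergent AEs (PTEAEs) for the last 4 weeks". The second label is then defined: "A PTEAE is defined as an event that first occurs or worsens in severity after the active-treatment phase (after Visit 5"), with the interval from first dose to Visit 5 as its baseline. On the tables it says: "PTEAEs will be summarized by Preferred Term and by Preferred Term within System Organ Class in participants who received LY3526318".

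SAP 6.1 uses the terms differently. It sets up a post active-treatment population made up of everyone who has not discontinued by Visit 5, with no restriction by arm, and says: "For treatment-emergent adverse events (TEAEs), participants in the post active-treatment population will be analyzed according to the treatment they receive" in the first phase. It promises adverse event reporting separately for the last 4 weeks and adds: "Some AEs may be reported for the entire 8 weeks if necessary".

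The only definition of a TEAE in the two documents is in the protocol's abbreviations appendix (10.5). It ties the term to a treatment period without giving its length. The protocol synopsis (1.1) describes double-blind treatment as lasting 8 weeks. General adverse event rules are left to the CPMP SAP Version 5, which is not among the documents reviewed.

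**The concern.** The registry rule appears not to have been adapted to this study's two-phase adverse event scheme. If a late non-serious event is a PTEAE and not a TEAE, it has no registry category, whereas a serious event on the same day does. The two registry tables would then cover different follow-up, and a reader of the public record would have no way to see it.

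The weeks at issue matter. SAP 5.1 states that the LY3526318 arm moves to placebo on the day of Visit 5, so Weeks 5 to 8 are where off-drug or delayed effects would show. Interpreting such events needs the concurrent placebo arm, and the PTEAE summary in 6.12.2 does not provide for it.

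**Working it through.** **Step 1: where each kind of event goes.** Two readings of TEAE are set side by side. Reading A takes the reporting windows in SAP 6.12.2 as the definition. Reading B takes the protocol glossary together with the 8-week treatment period.

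| Event | Reading A (TEAE = Weeks 1 to 4) | Reading B (TEAE = Weeks 1 to 8) |
|---|---|---|
| Serious, any week | Serious table | Serious table |
| Non-serious, treatment-emergent in Weeks 1 to 4, continuing unchanged | 'Other' | 'Other' |
| Non-serious, treatment-emergent in Weeks 1 to 4, worse after Visit 5 | 'Other' for the first onset; the worsening is a PTEAE and not counted | 'Other'; whether the worsening is a second event is not stated |
| Non-serious, new after Visit 5 | Neither table | 'Other', and also a PTEAE |

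The readings give different registry tables, and 6.19 does not say which applies. Its sentence that adverse event reporting agrees with the study report and manuscripts leans towards the 6.12.2 windows but does not settle the matter. Only events that are new or worse after Visit 5 are affected.

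The number at risk also depends on the choice. The post active-treatment population in 6.1 leaves out participants who stopped by Visit 5, so the denominator for Weeks 5 to 8 differs from the one for the whole period.

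**Step 2: the placebo arm.** SAP 6.1 places both arms in the post active-treatment population and analyses them by first-phase treatment. SAP 6.12.2 summarises PTEAEs "in participants who received LY3526318". The first implies a two-arm table for Weeks 5 to 8; the second provides for one arm.

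**Step 3: illustration of size.** The plan states no figure to reproduce, and the documents give no event rates. The incidences below are therefore assumed. Let p8 be the 8-week incidence of a term and s the share of the 8-week cumulative hazard that falls in Weeks 5 to 8. With complete follow-up, the incidence in Weeks 1 to 4 is

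p4 = 1 − (1 − p8)^(1 − s).

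At constant hazard s = 4/8 = 0.5:

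- p8 = 6%: p4 = 1 − 0.94^0.5 = 3.05%, so 1 − 3.05/6 = about 49% of affected participants are not shown.
- p8 = 8%: p4 = 1 − 0.92^0.5 = 4.08%.
- p8 = 10%: p4 = 1 − 0.90^0.5 = 5.13%.

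For p8 = 6% with other shares, p4 is 4.53% at s = 0.25 and 1.53% at s = 0.75.

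If the optional 5% threshold were used, the 8-week incidence needed for a term to reach 5% in Weeks 1 to 4 is 1 − 0.95^(1/(1 − s)):

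- s = 0.25: 6.6%
- s = 0.5: 1 − 0.95² = 9.75%
- s = 0.75: 1 − 0.95⁴ = 18.6%

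**The case against.** The strongest reply is that no visible text defines a TEAE as confined to Weeks 1 to 4. Section 6.12.2 sets a reporting window for study tables and defines only the PTEAE. The two labels use different baselines (pretreatment, and first dose to Visit 5), and nothing makes them mutually exclusive. The glossary allows an 8-week window, SAP 6.1 speaks of TEAEs in the post active-treatment population, and the governing definition may be in the CPMP SAP. All of this stands. A reader might infer that late non-serious events are definitely lost from the registry; the documents do not support that certainty.

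A reader might also infer that the placebo arm has no adverse event table at all for Weeks 5 to 8. That goes too far. SAP 6.1 promises adverse event reporting for the last 4 weeks without restricting it by arm, and 6.12.2 restricts only the PTEAE summary by Preferred Term and System Organ Class. What is established is that the two sections do not fit together.

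Third, treating serious and other events differently with respect to treatment emergence is an explicit rule in 6.19 and not in itself an error. That is fair. The difficulty arises only when the rule meets this study's separate label for late events.

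Finally, the LY3526318 arm's late events do have a planned PTEAE summary, so they are not lost to the study's own safety tables. This limits the harm to the registry record and to the missing placebo comparison in that summary.

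The reply does not remove the ambiguity. The optional 8-week reporting in 6.1 is discretionary and not linked to the registry, so someone programming from 6.12.2 and 6.19 as written would leave these events out.

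**Conclusion.** The point holds as a conditional one and is minor. Applied with the 6.12.2 windows, 6.19 leaves non-serious events that are new or worse in Weeks 5 to 8 out of the registry tables in both arms, while it keeps serious events from the same weeks. Under the 8-week reading they are included, and the text does not choose between the two. Separately, the one-arm PTEAE summary in 6.12.2 does not agree with the two-arm population in 6.1.

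The number of events affected cannot be derived from the documents. Half of the 8-week period is at issue (4 of 8 weeks), but it would be wrong to infer that half of all non-serious events are lost: the figures above rest on assumed incidences, an assumed split of hazard and complete follow-up. The 5% cut matters only if that threshold is adopted and a term is below it in every arm. No efficacy analysis is touched.

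**What to change.** 1. In SAP 6.19, define 'Other' as any non-serious TEAE or PTEAE over the full 8-week double-blind period, so that it covers the same follow-up as serious events. State that each event is counted once, since one that is worse after Visit 5 can carry both labels, and give the matching number at risk.
2. In SAP 6.12.2, summarise PTEAEs for both randomised arms, using the post active-treatment population of 6.1 as the denominator.
3. Reconcile the use of TEAE in 6.1 with 6.12.2, stating the window in one place. If the CPMP SAP already fixes it at 8 weeks, a cross-reference is enough for this item, and including PTEAEs in item 1 does no harm because of the count-once rule.

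The cost is SAP wording, one more reporting period and a slightly longer event table.

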7.1. PKPD Analysis Planning

A limited number of prespecified individuals who are not part of the blinded study team and do not have direct site contact, data entry, or data validation responsibilities may receive access to unblinded data prior to an interim or final database lock in order to initiate the PK and/or PKPD model development processes. This will be described in the unblinding plan. Information that may unblind the study during the analyses will not be reported to study sites or the blinded study team until the study has been unblinded.

8. References

Bellamy N. The WOMAC Knee and Hip Osteoarthritis Indices: development, validation, globalization and influence on the development of the AUSCAN Hand Osteoarthritis Indices. *Clin Exp Rheumatol*. 2005;23(5 suppl 39):S148-S153.

Signature Page for VV-CLIN-060045 v1.0

Approval

PPD

13-Jun-2022 14:41:19 GMT+0000

Signature Page for VV-CLIN-060045 v1.0

Approved on 13 Jun 2022 GMT
